The REDUCE-I Pilot Trial: REDucing the Utilization of CEsarean sections with Induction

Protocol ID: REB21-0614

NCT05037617

Version 3, October 15, 2021

The REDUCE-I Pilot Trial: REDucing the Utilization of CEsaean sections with Induction

BACKGROUND: The cesarean section (CS) epidemic appears to be continuing unabated and rising rates are being observed in the developing world. Recent data suggests that 21% of births worldwide are by CS and that this rate has doubled since 2000(1). While there is no doubt that CS is lifesaving in many circumstances for both mothers and babies, CS rates have risen significantly without any corresponding improvement in outcomes. CS, while protective of some pelvic floor outcomes, increases the rates of abnormal placentation in subsequent pregnancies, which increases the risk of severe maternal morbidity and hysterectomy(2). Reducing the risk of CS has proved challenging, and no clearly effective interventions have been identified in clinical trials(3, 4). Modelling studies suggest that the target population to reduce the overall CS rate should be first time mothers(5).

Currently the rate of CS in first time mothers with singleton fetuses ≥ 35 weeks with cephalic presentation being induced in Alberta is 32.6%(6). This has increased from 23.1% in 1992 and a recent study from our group found that increasing CS for fetal distress are the most important factor in explaining this rise(7). Induction of labor often overstimulates uterine contractions (hyperstimulation) and can lead to fetal distress. Therefore, an intervention to decrease uterine hyperstimulation may lead to a reduction in fetal distress and therefore CS. Additionally, uterine hyperstimulation can lead to the reduction of oxygen transport to the fetus potentially leading to asphyxia and hypoxic-ischemic encephalopathy (HIE) which can result in chronic neurodevelopmental impairment.

For the vast majority of women who are induced in Alberta (and worldwide), this is accomplished by intravenous oxytocin. An approach that could reduce uterine hyperstimulation with induction of labor is to discontinue the oxytocin infusion once the active phase of labor is reached. This is consistent with bench research that shows that oxytocin stimulates prostaglandin production in the chorio-decidua, which induces positive feedback loops to continue production(8). Furthermore, this idea has been tested in a number of small single centre clinical trials with encouraging results. The 10 trials to date have been summarized by two meta-analyses(9, 10). The number of randomized subjects was modest $n=1,538$ and the sample sizes ranged from 100-250. Most of trials were not of high quality with either high or unclear risk of bias. Only two of the trials were in populations comparable to Canada: one in Europe and one in the USA(11, 12). All trials that reported CS rates documented a reduction with oxytocin discontinuation; pooled OR 0.64 (0.48–0.87). The USA trial observed a reduction in the rate of CS with oxytocin discontinuation compared to continuing from 19.2% (24/125) to 25.2% (32/127) and the European trial the rates were 15% (15/100) vs 22% (22/100). The baseline rates of CS are comparable to our population and the differences they observed were clinically significant. The meta-analyses also observed reductions in the rates of uterine hyperstimulation with oxytocin discontinuation 0.53 (0.33–0.84). While these results are promising, a definitive large randomized controlled trial (RCT) is required to assess important safety outcomes. We propose an initial small pilot study, which will allow us to refine our protocol and will ensure the success of a large multi-centre cluster RCT. Additionally, we also wish to examine serial urine prostaglandin (PG) metabolite levels in a subset of the study population. Our group has completed a large study of PG metabolites (unpublished data) in over 200 women pre-labor and in labor. We have found that prostaglandin F and E metabolites are increased during induced and

Ethics ID: REB21-0614

Study Title: The REDUCE-I Pilot Trial: REDucing the Utilization of CEsaean sections with Induction

PI: [name]

Version 3 & Version date: October 15, 2021

Page 2 of 8

The REDUCE-I Pilot Trial: REDucing the Utilization of CEsarean sections with Induction

spontaneous labor. We hypothesize that patients who do not need oxytocin restarted may have higher levels or will not have a drop in their urinary PG metabolites. This data could help with improving compliance in future trials. This will also permit a precision medicine approach whereby in the larger trial, the intervention can be offered to those women most likely to benefit.

AIMS: In this REDucing the Utilization of Cesarean sections with Induction (REDUCE-I) Pilot Trial, we propose to answer the following question: Does discontinuation of oxytocin during the active stage of labor (≥ 6 cm dilation) decrease the rate of cesarean section (CS) in induced primiparous women, at term (≥ 37 weeks), with a cephalic presenting singleton fetus without increasing maternal or neonatal morbidity?

METHODS: The REDUCE-I Pilot Trial is a randomized controlled trial (RCT).

Proposed interventions: We will use the modern definition to define the active stage of labor to be ≥ 6 cm dilation(13). The intervention will be to stop oxytocin infusion when a dilation of ≥ 6 cm has been documented. The intervention will be continued until delivery unless contractions decrease to less than 2 in 10 minutes or if no further cervical dilation is noted 4 hours after discontinuation.

Randomization: A computer-generated random allocation sequence will be created by the study statistician. Randomization will stratified by need for cervical ripening and randomization will be blocked. Randomization will take place prior to the initiation of oxytocin.

Blinding: Once a patient is found to be ≥ 6 cm dilation, the study medication will be initiated. Pharmacy will make up identical vials of oxytocin or saline, which will be numbered according to the random allocation sequence created by the study statistician. Nurses will use the blinded vials for ongoing infusion. Patients and caregivers will be blinded.

Inclusion/exclusion criteria: Primiparous women 18 years old or older, at term (≥ 37 weeks) with a cephalic presenting singleton fetus undergoing induction of labor with oxytocin. Multiple pregnancies and known fetal congenital or chromosomal anomalies will be excluded.

Duration of treatment: The treatment period will continue until delivery. If the frequency of the patient's contractions are reduced to less than 2 in 10 minutes or there has been no change in dilation for 4 hours then oxytocin can be restarted.

In the event a physician or midwife makes a decision to stop the study medication, they have the option to become unblinded by making a request to pharmacy to make it easier for them to know at what dose to continue or re-start oxytocin.

Duration of follow up: Maternal and neonatal follow up until discharge. Postpartum readmission and outcomes will be obtained up to 4 weeks postpartum.

Ethics ID: REB21-0614

Study Title: The REDUCE-I Pilot Trial: REDucing the Utilization of CEsarean sections with Induction

PI: [name]

Version 3 & Version date: October 15, 2021

Page 3 of 8

The REDUCE-I Pilot Trial: REDucing the Utilization of CEsaean sections with Induction

Primary outcomes: 1) CS in labor. 2) Uterine hyperstimulation (occurrence of >5 contractions in 10 minutes). 3) Proportion of screened subjects who agree to enroll in the trial.

Secondary outcomes: Adverse neonatal and maternal outcomes including:

Neonatal: a) Perinatal death; b) Neonatal asphyxia: intrapartum stillbirth or neonatal death from asphyxia (Perinatal Society of Australia and New Zealand coding)(14) or NICU admission and at least two of: i. Apgar score of ≤ 5 at 10 minutes; ii. Mechanical ventilation or chest compressions for resuscitation within 10 minutes; iii. Cord pH < 7.00 (venous or arterial), or arterial base excess ≥ 12 at birth; c) moderate or severe asphyxia (Sarnat)(15) or meets criteria for therapeutic cooling; and d) sepsis or suspected sepsis.

Maternal: a) postpartum hemorrhage (PPH); b) blood transfusion; c) postpartum uterine artery/pelvic artery embolization; d) postpartum hysterectomy; and e) postpartum maternal intensive care unit (ICU) admission.

Compliance: Duration of oxytocin discontinuation. Rate of reintroduction of oxytocin infusion.

Urine Prostaglandin metabolites: Urine samples will be collected every 2 hours during labor from a minimum of 13 women in the intervention group and a minimum of 13 women in the control group. Samples will be aliquoted, frozen, and stored at -80°C prior to analysis. The following five assays will be performed: Prostaglandin E2 ELISA kit (Cayman 514010); Prostaglandin E2 metabolite ELISA kit (Cayman 514531); Prostaglandin F 2α ELISA Kit (Cayman 516011), PGF 2α metabolite, 13,14-dihydro-15-keto Prostaglandin F 2α ELISA Kit (Cayman 516671); and creatinine ELISA kit. Assays will be performed according to manufacturer instructions with appropriate dilutions.

Measurement of Outcomes: The primary and secondary outcomes will be obtained by detailed chart review by an experienced nurse blinded to allocation. To assess neonatal outcomes, such as hypoxic-ischemic encephalopathy (HIE), data will be obtained by linkage to a specialized asphyxia database in Calgary. This database has collected data on all neonates in Calgary diagnosed with HIE since 2010. Loss to follow-up is not applicable for the current trial as data on all hospital-based deliveries are routinely captured in the medical chart.

Sample Size: The proposed sample size is 200. Approximately 1250 primiparous women are induced each year at Foothills Medical Centre; their CS rate is approximately 30%. A sample of 200 subjects has 30% power to detect an absolute difference of 10% in CS rate and 44% power to detect a difference consistent with previous trials. While under-powered for clinical outcomes, this pilot RCT will allow us to determine an effect size in our population (which will be required to perform a sample size calculation for a larger trial) and will allow us to assess the feasibility of moving forward with a larger study.

Ethics ID: REB21-0614

Study Title: The REDUCE-I Pilot Trial: REDucing the Utilization of CEsaean sections with Induction

PI: [name]

Version 3 & Version date: October 15, 2021

Page 4 of 8

The REDUCE-I Pilot Trial: REDucing the Utilization of CEsaean sections with Induction

Recruitment: We would expect approximately 1250 primiparous women to be induced at Foothills Medical Centre (FMC) over the study period, therefore, we are anticipating approximately a 16% recruitment rate.

Compliance: Compliance to the treatment is a potential problem. Not all previous studies reported compliance but it is noteworthy that in the USA study that oxytocin was continued in 25% of subjects randomized to discontinuation and restarted in a further 25%(12). This may have been due to concerns regarding the potential adverse effects of longer labor. We note that all the previous studies were performed prior to the release of recent guidelines on labor management (13), which advocated for accepting slow progress in labor and allowing longer labors. These recent guidelines were the intervention we tested in the REDUCED trial, a clustered multi-centre trial which is now completed. Our results did not find any evidence of increased maternal or neonatal risks with longer labors. The intervention site for this study (Foothills Medical Centre [FMC]) was a control site but we plan to move toward adoption of the guidelines at FMC over the next 3-6 months (pandemic permitting). We anticipate that our data will alleviate physician concerns regarding longer labors and encourage patience in managing labor.

Location: Two academic centres will be used for the pilot: FMC in Calgary will be the treatment site, and Royal Alexandra Hospital in Edmonton will be used as a contemporaneous non-intervention control site.

Statistical Analysis: The analysis will be conducted independently by the study statistician ([name]). The primary outcome will not be changed during analysis. The trial, with an explicit statement of the primary outcome, will be registered at clinicaltrials.gov. For dichotomous outcomes relative risks will be calculated and Fisher exact test will be used to assess statistical significance. For continuous outcomes mean differences will be assessed with t-tests after appropriate transformations. Sub-group analysis will be performed by need for cervical ripening. The analyses will be conducted after recruitment for the pilot study has been completed. We will conduct a differences-in-differences analysis using contemporaneous control data from the Royal Alexandra Hospital in Edmonton to monitor for temporal trends in outcomes and changes in labor management.

Timeline: This study will be completed in two years (see figure).

EXPERTISE, EXPERIENCE & RESOURCES: We are a strong interdisciplinary and well-established team with expertise in obstetrics, epidemiology, neonatology, molecular biology, clinical trials, and biostatistics. The principal applicant ([name], Obstetrician/Epidemiologist) will be responsible for directing trial. The co-principal applicant ([name], Epidemiologist) will co-manage the trial and will analyze the results of the Childbirth Experience Questionnaire 2 (CEQ2). The data will be collected and prepared for analysis by [name] and [name] (Epidemiologist for APHP). The

Ethics ID: REB21-0614

Study Title: The REDUCE-I Pilot Trial: REDucing the Utilization of CEsaean sections with Induction

PI: [name]

Version 3 & Version date: October 15, 2021

Page 5 of 8

The REDUCE-I Pilot Trial: REDucing the Utilization of CEsaean sections with Induction

neonatal HIE data will be obtained by the study neonatologist ([name]). The co-principal applicant, [name] will supervise the measurement of the urinary prostaglandins. The analysis will be carried out independently by the study statistician ([name]). Two clinical collaborators, [name] and [name] from the obstetrics group at FMC will aid in recruitment.

ALIGNMENT WITH THE CHW STRATEGY AND RELEVANT PROJECT METRICS:

Our research project is aligned with the Maternal and Child Health research program, which is outlined in University of Calgary’s Child Health and Wellness Strategy(19). Safely decreasing the cesarean section rate

in induced women will benefit maternal and infant health. As described above, cesarean sections increase the risk of severe maternal morbidity and hysterectomy, and CS may impact the development of the normal neonatal microbiome, which may have long term effects on child health. In addition,

	Q 1	Q 2	Q 3	Q 4	Q 5	Q 6	Q 7	Q 8
Ethics & operational approvals	x							
Recruit participants and conduct trial		x	x	x	x	x		
Laboratory analyses							X	
Data cleaning and analysis							X	X
Manuscript preparation								x

discontinuation of oxytocin during the active phase of labor may decrease the risk of neonatal asphyxia, which can have devastating and long-term consequences to child health.

Our project is relevant to the Better Beginnings grand challenge area in child health and wellness, which is related to optimizing maternal, fetal, newborn and child health with accurate prediction, prevention, and interventions. If successful, this trial will prevent cesarean sections, which will provide infants the best start in life and improvements to maternal health. We will be utilizing two approaches to solving this grand challenge. As a registry-based trial, we will be ‘harnessing big data for optimal child outcomes’ given that we are using the Alberta Perinatal Health Program database, as well as the southern Alberta asphyxia database, to obtain most of the data for our project. Secondly, we will be ‘transforming health care for children and families’ as this clinical intervention is designed to change the way care is delivered.

SUSTAINABILITY: If REDUCE-I suggests a safe reduction in the CS rates, we will apply to CIHR for a Project Scheme grant for a multi-center randomized controlled trial to test this intervention in our trial network from the REDUCED trial.

Ethics ID: REB21-0614

Study Title: The REDUCE-I Pilot Trial: REDucing the Utilization of CEsaean sections with Induction

PI: [name]

Version 3 & Version date: October 15, 2021

The REDUCE-I Pilot Trial: REDucing the Utilization of CEsaean sections with Induction

REFERENCES

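### Women are randomized before oxytocin but the arms differ only from 6 cm, so cesareans in labor before 6 cm dilute the comparison; assigning the vial at 6 cm, or adding an analysis of women who reach it, is a cheap improvement

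*Combined protocol and SAP*

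**What the plan says.** All references are to the combined protocol and SAP.

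- **Randomization:** "Randomization will take place prior to the initiation of oxytocin". It is blocked and stratified by need for cervical ripening.
- **Blinding:** "Once a patient is found to be ≥ 6 cm dilation, the study medication will be initiated". The pharmacy prepares identical numbered vials, and patients and caregivers are blinded.
- **Proposed interventions:** "The intervention will be to stop oxytocin infusion when a dilation of ≥ 6 cm has been documented".
- **Inclusion/exclusion criteria:** primiparous women at term "with a cephalic presenting singleton fetus undergoing induction of labor with oxytocin". Reaching 6 cm is not required.
- **Aims:** "Does discontinuation of oxytocin during the active stage of labor (≥ 6 cm dilation) decrease the rate of cesarean section (CS) in induced primiparous women".
- **Outcomes:** "Primary outcomes: 1) CS in labor". No dilation threshold is attached.
- **Statistical Analysis:** "For dichotomous outcomes relative risks will be calculated and Fisher exact test will be used to assess statistical significance". No analysis population is named, and the only subgroup is need for cervical ripening.
- **Sample Size:** 200 women. The planning rate is for all induced primiparous women at the treatment site: "their CS rate is approximately 30"%. The pilot is also to supply an effect size for sizing a larger trial.

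**The concern.** Nothing in the plan separates the arms before 6 cm. A woman who has a cesarean in labor before then has been randomized, never receives a study vial, and would still be counted if all randomized women are analyzed. That is the usual reading when no exclusion is written. Such events occur at the same expected rate in both arms, so they add to both sides of the RR without carrying information on discontinuation.

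Two things are at stake. Some of an already small amount of power is lost. And the effect size taken from the pilot becomes a mixture of the treatment's effect and the share of cesareans that happen too early to be affected. If the number delivered before 6 cm is not reported, a later reader cannot tell a weak treatment from a diluted one.

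**Working it through.** **The plan's own figure.** The Sample Size section gives 30% power for a 10-point difference from 30%. Assuming 100 per arm and two-sided alpha 0.05 (neither is stated), 30% versus 20% gives 31.3% by Fisher's exact test, 31.1% with a continuity correction and 37.1% uncorrected. The stated 30% therefore reproduces. It takes the full 10 points among all randomized women and makes no allowance for cesareans before 6 cm.

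**Inputs.** Control cesarean rate 30% (Sample Size). Pooled odds ratio 0.64 (Background), assumed here to act only after 6 cm. Share *f* of control cesareans occurring before 6 cm: not in the documents, so a range of 10% to 60% is shown.

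**Formulas.**
- Cesarean before 6 cm: 0.30*f*. Reaching 6 cm: 1 − 0.30*f*.
- Control risk after 6 cm: p = 0.30(1 − *f*)/(1 − 0.30*f*).
- Treated risk after 6 cm: q = 0.64p/(1 − p + 0.64p).
- RR after 6 cm: R = q/p. RR in all randomized: *f* + (1 − *f*)R, which is closer to 1 than R whenever *f* > 0 and R ≠ 1.
- Power (uncorrected): Φ{[d − 1.96√(2p̄(1 − p̄)/n)] / √([p₁(1 − p₁) + p₂(1 − p₂)]/n)}, where d is the risk difference, p̄ the mean risk and n the number per arm.

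**Worked case, *f* = 40%.** Before 6 cm: 0.30 × 0.40 = 0.12. Reaching 6 cm: 0.88. p = 0.18/0.88 = 0.2045. q = 0.1309/0.9264 = 0.1413. R = 0.1413/0.2045 = 0.69. Overall treated risk: 0.12 + 0.88 × 0.1413 = 0.244, so the overall RR is 0.244/0.30 = 0.81.

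| *f* | Reach 6 cm, per 100 | p | q | RR after 6 cm | RR all randomized | Power, all (100 per arm) | Power, reaching 6 cm | Ratio of z² |
|---|---|---|---|---|---|---|---|---|
| 10% | 97 | 27.8% | 19.8% | 0.71 | 0.74 | 24% | 26% | 1.10 |
| 20% | 94 | 25.5% | 18.0% | 0.70 | 0.76 | 20% | 24% | 1.22 |
| 40% | 88 | 20.5% | 14.1% | 0.69 | 0.81 | 14% | 20% | 1.58 |
| 60% | 82 | 14.6% | 9.9% | 0.68 | 0.87 | 9% | 15% | 2.30 |

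Both power columns concern the same 200 randomized women. With *f* = 0 the same formula gives 27.7%. The plan's 44%, for a difference consistent with previous trials, is not used here.

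**Effect on sizing the larger trial.** Total N for 80% power is 2n, with n = [1.96√(2p̄(1 − p̄)) + 0.842√(p₁(1 − p₁) + p₂(1 − p₂))]²/d². At *f* = 40%:
- all-randomized RR with the all-induction rate (30% vs 24.4%): 2,008;
- RR after 6 cm with the rate after 6 cm (20.5% vs 14.1%): 1,122 women reaching 6 cm;
- RR after 6 cm wrongly paired with the all-induction rate (30% vs 0.69 × 30% = 20.7%): 690, far too few.

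**Consents for 200 randomized at 6 cm.** 200/(1 − 0.30*f*) gives about 206, 213, 227 and 244, or 16.5% to 19.5% of about 1250 inductions, against the planned 200/1250 = 16%. These are minimums: they allow only for cesareans before 6 cm, not for women whose oxytocin is no longer running at that point.

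**The case against.** The strongest reply is that the all-randomized comparison answers the question asked. The Aims, the eligibility criteria and the 30% planning rate all refer to induced primiparous women, and for them the RR is unbiased. This stands. A reader might infer that the planned analysis is biased or wrong; the documents do not support that. The dilution is relative to a different target, the effect in women who can receive the intervention.

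A reader might also infer that every cesarean before 6 cm enters the comparison. That goes too far. The outcome is cesarean in labor, which is not defined further, so a failed induction might be judged not in labor and not counted. Inclusion of the rest is inferred from the absence of a stated analysis set.

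The size is uncertain and may be small. At a 5% share the gain in z² is only 1.05-fold. The Background does not say when the earlier trials randomized or whom they analyzed; if 0.64 already includes early cesareans, the calculation discounts it twice. The z² ratios look better than the power gain of a few points in a pilot that calls itself under-powered. Nor does restriction make the RR more precise: at a 40% share the approximate 95% interval is 0.52 to 1.29 in all randomized women and 0.36 to 1.34 in those reaching 6 cm.

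Finally, the Background foresees a cluster trial. If that trial counts cesareans in all induced women, the all-randomized effect is its correct planning input. This limits how the post-6 cm estimate should be used, but it does not remove the value of reporting both.

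The objection that restriction breaks randomization has little force here. Care is the same and allocation is blinded until 6 cm, so reaching 6 cm should not depend on arm.

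**Conclusion.** The point holds as a cheap improvement, not as an error. Cesareans in labor before 6 cm cannot respond to allocation and move the all-randomized RR toward 1. Under the stated assumptions the shift runs from 0.71 to 0.74 at a 10% share up to 0.68 to 0.87 at a 60% share, and restricting the analysis recovers about 2 to 6 points of power.

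The direction follows from the design. The size depends on a share that the documents do not give, on an odds ratio of 0.64 acting only after 6 cm, on 1:1 allocation, and on every woman without an early cesarean reaching a documented 6 cm with oxytocin running. The power figures are uncorrected and would be lower with the planned Fisher test. The main practical loss is an effect size that cannot be interpreted or carried forward without knowing how many women were delivered before 6 cm.

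**What to change.** **Preferred.** Keep consent and recording of ripening status before oxytocin, but assign the next numbered vial within stratum when at least 6 cm is documented with oxytocin running. The vials are already numbered and started at that point, so only the timing of assignment changes. Cost: protocol wording, and at least about 206 to 244 consents for 200 randomized. The target population becomes women who reach 6 cm, and the Aims should say so. Report the proportion of consented women who reach 6 cm as a feasibility result.

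**If randomization stays early.**
- State the analysis set and define cesarean in labor.
- Keep the all-randomized comparison and prespecify alongside it a cesarean comparison in all women who reach a documented 6 cm and are due to start the vial. Define this set without regard to arm or to whether the vial was in fact started.
- Report by arm the number delivered before 6 cm, which also checks that reaching 6 cm was balanced.

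Cost: a few sentences of analysis text. About 3% to 18% of randomized women fall outside the added set over the 10% to 60% range.

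**Either way.** When sizing the larger trial, pair the post-6 cm RR with the post-6 cm cesarean rate, and an all-randomized RR with the all-induction rate. Do not mix them.

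### The 44% power for an effect like that of earlier trials has no stated effect size, and no cesarean point estimate printed in the protocol reproduces it (pooled OR 0.64 gives about 23%)

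*Combined protocol and SAP*

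**What the plan says.** The Sample Size section fixes the total at 200 and says of first-time mothers induced at the treatment site that "their CS rate is approximately 30"%. It then gives two powers in one sentence: "30% power to detect an absolute difference of 10% in CS rate and 44% power to detect a difference consistent with previous trials". No arm-specific rates accompany the second power, and neither power comes with an alpha, sidedness, allocation ratio or test.

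The earlier CS results are in the Background. The pooled result is "pooled OR 0.64 (0.48–0.87" (the bracket is the interval). For the two trials judged comparable to Canada the protocol reports "19.2% (24/125) to 25.2% (32/127) and the European trial the rates were 15% (15/100) vs 22% (22/100"; the lower rate in each pair is read here as the discontinuation arm. The Background also reports "reductions in the rates of uterine hyperstimulation with oxytocin discontinuation 0.53 (0.33–0.84", which concerns a different outcome, and a provincial CS rate: "cephalic presentation being induced in Alberta is 32.6%(6".

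The Statistical Analysis section plans Fisher's exact test for binary outcomes.

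**The concern.** The two powers appear to be in the wrong order. For a reduction from the same control rate, with the same test and sample size, a smaller difference has less power. At 30%, each printed CS point estimate is a smaller difference than 10 points, yet the effect attributed to earlier trials is given more power (44%) than 10 points (30%).

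The 44% is the only power given for the effect that motivates the trial. If the pooled OR is what was meant, the figure is about twice what the planned test delivers. As written, a reader cannot tell which effect, test or alpha it belongs to.

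**Working it through.** **Inputs.** From the protocol: total 200 and control rate 30% (Sample Size); OR 0.64 with interval 0.48 to 0.87, 24/125 vs 32/127, and 15/100 vs 22/100 (Background); Fisher's exact test (Statistical Analysis). Assumed because not stated: 100 per arm, two-sided alpha 0.05. No dropout is applied, since the protocol says loss to follow-up does not arise.

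**Method.** Exact power is the sum, over all outcomes (x, y), of Bin(x; 100, p1) × Bin(y; 100, p2) for those tables that the test rejects at 0.05. Uncorrected chi-square is shown for comparison.

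**Step 1: the plan's first figure.** 30% vs 20% gives 31.3% by Fisher and 37.1% by chi-square. The stated 30% fits the planned Fisher test.

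**Step 2: carry the printed effects to a 30% control rate.**
- Pooled OR: p2 = (0.3/0.7 × 0.64) / (1 + 0.3/0.7 × 0.64) = 0.2743/1.2743 = 0.2152, a fall of 8.5 points.
- For comparison, a 10-point fall is OR (0.2/0.8)/(0.3/0.7) = 0.583, a stronger effect than 0.64.
- USA trial: difference 6.0 points; OR (24/101)/(32/95) = 0.705; RR (24/125)/(32/127) = 0.762.
- European trial: difference 7.0 points; OR (15/85)/(22/78) = 0.626; RR 15/22 = 0.682.

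**Step 3: power for each.**

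| Effect at 30% control | Intervention rate | Fall (points) | Fisher | Chi-square |
|---|---|---|---|---|
| 10 points | 20.0% | 10.0 | 31.3% | 37.1% |
| Pooled OR 0.64 | 21.5% | 8.5 | 22.6% | 27.6% |
| European RR 0.682 | 20.5% | 9.5 | 28.5% | 34.1% |
| European OR 0.626 | 21.1% | 8.9 | 24.6% | 29.8% |
| European difference | 23.0% | 7.0 | 15.9% | 20.0% |
| USA RR 0.762 | 22.9% | 7.1 | 16.5% | 20.7% |
| USA OR 0.705 | 23.2% | 6.8 | 15.1% | 19.1% |
| USA difference | 24.0% | 6.0 | 12.3% | 15.8% |

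No printed CS point estimate reaches the power for 10 points.

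**Step 4: what 44% would require.** By Fisher it needs about 30% vs 18.1%, an 11.9-point fall, OR about 0.52 (44.1%). Across the quoted interval, Fisher power runs from 5.3% (OR 0.87) to 51.7% (OR 0.48). With OR 0.64 kept, 44% needs about 195 per arm (390 women), and 10 points would then have about 59%.

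**Step 5: can other assumptions rescue it?**
- *Baseline.* Fisher power for OR 0.64 does not exceed 31.6% at any control rate from 10% to 90%. At the 32.6% provincial rate, 10 points gives 29.7%, OR 0.64 gives 24.0%, and the European RR (now 10.4 points) gives 31.9%. The ordering argument is therefore exact only at the stated 30%, but none of these comes near 44%.
- *One-sided 0.05.* The ceiling for OR 0.64 rises to 42.3%, but 30% vs 20% then gives 43.7%, not 30%.
- *Test, alpha and allocation.* In 100 designs with N = 200 (control arm 67, 80, 100, 120 or 133; two-sided Fisher, chi-square and Yates, one-sided Fisher and chi-square; alpha 0.01, 0.025, 0.05, 0.10), no printed CS point estimate at 30% reached the power for 10 points. In the 10 designs giving 28.5% to 31.5% for 30% vs 20%, the largest power for any printed estimate was 28.5%, and OR 0.64 gave 20.8% to 22.7%.

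**Step 6: possible origins, none established.** Reading 0.64 as a risk ratio (30% vs 19.2%) gives 36.4% by Fisher and 42.6% by chi-square. Applying the hyperstimulation ratio 0.53 as an OR to the 32.6% CS rate gives 43.6%, but that mixes two outcomes. Hyperstimulation itself is a co-primary outcome ("2) Uterine hyperstimulation (occurrence of >5 contractions in 10 minutes"), but its baseline is not printed. Over assumed baselines of 10% to 50%, Fisher power for 0.53 runs from 14.8% to 55.1% as an OR and from 16.6% to 91.2% as a risk ratio.

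**The case against.** The strongest reply is that the sentence does not name the pooled estimate. It speaks only of agreement with earlier trials. An OR of about 0.52 lies inside the printed interval, so read literally the statement can be true. The Background also mentions ten trials and two meta-analyses but prints only one pooled CS estimate and two trials' rates, so the intended effect may come from a source not shown. What stands is that the cause is unknown and 23% is the right replacement only if the pooled OR was meant. But a phrase that covers powers from 5.3% to 51.7% does not define a power, and unprinted rates cannot support a printed figure.

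A second reply is that one method does come near both figures. An uncorrected test gives 31.6% for a 10-point increase (30% vs 40%) and 42.5% to 43.1% for 0.64 taken as a risk ratio. This requires the OR label in the Background to be wrong and the 10 points to run against the stated aim to "decrease the rate of cesarean section (CS) in induced primiparous women". For a 10-point decrease the same test gives 37%, not 30%.

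Third, this is a pilot. The Sample Size section concedes low power for clinical endpoints, N = 200 is not derived from 44%, and the larger trial is to be sized from the pilot's own effect. That is correct, and it limits the severity.

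**Conclusion.** The concern holds, as a minor one. The effect behind the 44% is not specified, and no CS point estimate printed in the protocol yields that power at the stated 30% rate together with about 30% for 10 points. With 100 per arm and two-sided 0.05 (both assumed), the planned Fisher test gives 22.6% for the pooled OR and at most 28.5% for any printed CS point estimate. If the pooled OR was meant, the stated power is overstated by about 21 points (44 − 22.6 = 21.4). Confidence is high that the figure does not follow from the printed estimates. Which effect was intended, and how 44% arose, cannot be settled from the document. No design or analysis decision depends on it.

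**What to change.** In the Sample Size section, state for both powers the rate in each arm, alpha, sidedness, allocation and test, and recompute the second with the planned Fisher test. The replacement depends on the effect meant:
- If the pooled OR 0.64 is meant, replace 44% with about 23% (30% vs 21.5%, 100 per arm, two-sided 0.05).
- If a check of the source shows that 0.64 is a risk ratio, correct its label in the Background and state about 36% (30% vs 19.2%).
- If another effect, another baseline or the hyperstimulation outcome is meant, name it and print its rates and Fisher power.

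The cost is one rewritten sentence and one check of the effect measure. The stated power will probably look less favorable. No extra patients are needed, and neither the design nor the analysis changes.
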